**Table 2-4 Notable ECG values**

ECG parameter (unit)	Clinically notable criteria
QTcF (ms)	Increase >30 and <=60 ms Increase >60 ms New >450 to <=480 ms New >480 to <=500 ms New >500 ms
QT (ms)	Increase >30 to <=60 ms Increase >60 ms New >450 to <=480 ms New >480 to <=500 ms New >500 ms
HR (bpm)	Increase >25% and HR >100 bpm Decrease >25% and HR <50 bpm
PR (ms)	Increase from baseline >25% and to a value > 200 ms New value of > 200 ms
QRS (ms)	Increase from baseline >25% and to a value > 120 ms New values of QRS > 120 ms

In addition, local ECGs are performed but not used for summary of QTc values. If abnormalities are observed based on these local ECGs, these abnormalities are to be reported and thus summarized as AEs.

#### 2.7.4.2 Vital signs

Notable vital sign values during on-treatment period will be summarized using the following criteria:

**Table 2-5 Notable vital sign values**

Vital sign (unit)	Clinically notable criteria	
	above normal value	below normal value
Systolic blood pressure (mmHg)	>=180 with increase from baseline of >=20	<=90 with decrease from baseline of >=20
Diastolic blood pressure (mmHg)	>=105 with increase from baseline of >=15	<=50 with decrease from baseline of >=15
Pulse rate (bpm)	>=100 with increase from baseline of >25%	<=50 with decrease from baseline of > 25%
Weight (kg)	Increase >=10% from baseline	Decrease >= 10% from baseline
Body temperature (°C)	>= 39.1	-

[figure not shown]
## 2.8 Pharmacokinetic endpoints

Pharmacokinetic endpoints will be analyzed and summarized by dose level of MBG453 (400 mg Q4W, 800 mg Q4W).

### 2.8.1 MBG453 and venetoclax drug concentrations

Pharmacokinetic analyses will be summarized for the MBG453 or venetoclax pharmacokinetic analysis set. MBG453 and venetoclax concentration data will be listed by dose level, subject, and visit/sampling time point. Descriptive summary statistics for MBG453 and venetoclax concentrations will be provided by dose level, visit/sampling time point, excluding concentrations at EOT, 30-day follow-up, 150-day follow-up visit and unscheduled visit. Summary statistics will include mean (arithmetic and geometric), SD, CV (arithmetic and geometric), median, minimum, and maximum, as well as the frequency (n, %) of concentrations below the lower limit of quantification (LLOQ) and reported as zero. Values below the LLOQ will be treated as missing for the calculation of the geometric means and geometric CV%. MBG453 and venetoclax concentration data obtained from samples collected outside of PK sample collection window as defined per protocol will be flagged and excluded for the summary statistics.

All concentration data for MBG453 vs. time profiles with arithmetic mean (+/- SD) and geo-mean will be displayed graphically, excluding concentrations at EOT, 30-day follow-up, 150-day follow-up visit and unscheduled visit.

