6.1.1 Investigational and control drugs

Table 6-1 Study Treatment

Investigational/ Combination Drug (Name and Strength)	Strength	Pharmaceutical dosage form and route of administration	Supply Type	Sponsor (global or local)
MBG453	100 mg in 1ml and/or 400 mg in 4 ml	solution in vial for i.v. infusion	Open Label	Sponsor (global)
Venetoclax	100 mg and/or 50 mg and/or 10 mg (or as per local supply)	tablet for oral use	Open Label	Sponsor (global) or provided locally (US)
Azacitidine*	as per local supply	solution for i.v. infusion or subcutaneous administration	Open Label	Provided locally

* Formulation for generic azacitidine as approved by local regulations

MBG453

MBG453 will be administered at a dose of 400 mg Q4W (safety run-in cohort 1) or 800 mg Q4W (safety run-in cohort 2 and expansion) via i.v. infusion over 30 minutes on Day 8 of every 28-day cycle.

If the alternative schedule is selected for azacitidine by the investigator, azacitidine and MBG453 will be given on the same day (day 8 of the 28-day cycle). Azacitidine should be administered first, followed by MBG453. The first dose of MBG453 should be administered after the subject has received at least 5 doses of azacitidine.

Further instructions for the preparation, dispensation, and administration of MBG453 are described in the Pharmacy Manual.

Venetoclax

Venetoclax film-coated tablets should be administered at a dose of 400 mg orally or corresponding reduced dose for concomitant use with P-gp inhibitors or moderate or strong CYP3A4 inhibitors (see [Table 6-3](#) and [Venclexta® \(Venetoclax\) USPI 2018](#)), once a day, on

each day of the 28-day cycle. Subjects should be instructed to swallow the tablets whole (tablets should not be crushed or broken), with water, at approximately the same time each day. The tablets should be taken with a meal (ideally at breakfast).

In Cycle 1, the dose of venetoclax will be ramped-up over a period of 3 or 4 days (C1D1 - C1D3 or C1D4) to achieve the dose of 400 mg per day (see [Table 6-2](#)), or corresponding reduced dose per day for concomitant with P-gp inhibitors or moderate or strong CYP3A4 inhibitors (see [Table 6-3](#) and [Venclexta® \(Venetoclax\) USPI 2018](#)). During the ramp-up period, venetoclax should be taken in the morning to facilitate laboratory monitoring. See [Section 8.4.4](#) for additional considerations during ramp-up and [Section 6.5.4.2](#). For guidance on prophylaxis and follow-up for suspected TLS.

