6.2.1.1 Permitted concomitant therapy requiring caution and/or action

Medications to be used with caution during study treatment in this study are listed below. Please also refer to Appendix 2 (see [Section 16.2](#)) for detailed guidance.

Strong or moderate CYP3A4 inhibitors and P-gp inhibitors: If, such therapy is necessary, it can be introduced, under the provision that the dose of venetoclax is reduced. Recommendation for venetoclax dose, when given in combination with strong CYP3A inhibitors (e.g., posaconazole, ketoconazole, conivaptan, clarithromycin, indinavir, itraconazole, lopinavir, ritonavir, telaprevir, and voriconazole), moderate CYP3A inhibitors (e.g., erythromycin, ciprofloxacin, diltiazem, dronedarone, fluconazole, and verapamil) or P-gp inhibitors (e.g., amiodarone, azithromycin, captopril, carvedilol, felodipine, quercetin, quinidine, ranolazine, and ticagrelor) are provided in [Table 6-3](#) below.

Table 6-3 Management of potential interactions of CYP3A and P-gp inhibitors with venetoclax

Co-administered Drug	Ramp-Up Phase	Steady Daily Dose (After Ramp-Up Phase)
Posaconazole	Day 1 - 10 mg Day 2 - 20 mg Day 3 - 50 mg Day 4 - 70 mg	Reduce venetoclax dose to 70 mg
Other strong CYP3A inhibitor	Day 1 - 10 mg Day 2 - 20 mg Day 3 - 50 mg Day 4 - 100 mg	Reduce venetoclax dose to 100 mg
Moderate CYP3A inhibitor or P-gp inhibitor	Day 1 - 50 mg Day 2 - 100 mg Day 3 - 200 mg	Reduce venetoclax dose to 200 mg (at least 50% reduction)

The venetoclax dosage that was used prior to concomitant use with a strong or moderate CYP3A inhibitor or a P-gp inhibitor should be resumed 2 to 3 days after discontinuation of the inhibitor. Subjects should be instructed to avoid grapefruit products, Seville oranges, and starfruit during treatment with venetoclax as they contain inhibitors of CYP3A4.

Strong or Moderate CYP3A4 inducers: Concomitant use of venetoclax with strong CYP3A inducers (e.g., carbamazepine, phenytoin, rifampin, St.John's wort) or moderate CYP3A inducers (e.g., bosentan, efavirenz, etravirine, modafinil, nafcillin) should be avoided. Alternative treatments with less CYP3A induction should be considered.

P-gp or BCRP substrates: Co-administration of narrow therapeutic index P-gp, or BCRP substrates (e.g., digoxin, sirolimus) with venetoclax should be avoided.

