## **Cumulative dose, dose intensity and relative dose intensity of venetoclax**

For venetoclax, as per protocol, the full dose will be adjusted due to the concomitant administration of CYP3A inhibitors or P-gp inhibitors. By this adjustment, the intended exposure to venetoclax is assumed to remain unchanged from clinical perspective (equivalent to full daily dose 400 mg). To this end,

- Cumulative dose will be calculated by two methods. The first one is actual cumulative dose which uses the “dose administered” in Study Treatment - Venetoclax eCRF (unadjusted method), and the second one is cumulative dose which uses the adjusted “dose administered” (400 mg/day), if administered with the concomitant CYP3A inhibitors or P-gp inhibitors (adjusted method). The first is to reflect the actual amount of venetoclax a patient receives, and the second is to reflect the actual exposure to venetoclax.
- Similarly, dose intensity will also be calculated by two methods: unadjusted and adjusted methods.
- Of note, planned dose intensity of venetoclax will only be calculated by the adjusted method and will be averaged in case the full dose changed during the ramp-up period.

For example, if a subject received a full dose of venetoclax at 400 mg during the first 2 cycles (including the ramp-up period), the dose interrupted in the next 14 days and then resumed to receive full dose of venetoclax at 200 mg with the concomitant CYP3A4 inhibitors or P-gp inhibitors during the subsequent 42 days (until the end of Cycle 4). So for this subject, his venetoclax dose/exposure can be summarized as follows:

	Unadjusted method	Adjusted method
Cumulative dose	$(100+200+300)+ 400 \times 25 \text{ days} + 400 \times 28 \text{ days} + 0 \times 14 \text{ days} + 200 \times 42 \text{ days} = 30200 \text{ mg}$	$(100+200+300)+ 400 \times 25 \text{ days} + 400 \times 28 \text{ days} + 0 \times 14 \text{ days} + 400 \times 42 \text{ days} = 38600 \text{ mg}$
Dose intensity	$30200/(28 \text{ days} \times 4) \times 28 \text{ days} = 7550 \text{ mg per 28 days}$	$38600/(28 \text{ days} \times 4) \times 28 \text{ days} = 9650 \text{ mg per 28 days}$
Planned dose intensity	-	$[(100+200+300) + 400 \times 25 \text{ days} + 400 \times 28 \text{ days} + 400 \times 14 \text{ days} + 400 \times 42 \text{ days}] / (28 \text{ days} \times 4) \times 28 \text{ days} = 11050 \text{ mg per 28 days}$
Relative dose intensity	-	$9650/11050 = 87.33\%$

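### Venetoclax pre-dose concentrations are summarised only by MBG453 dose level and visit, so inhibitor-adjusted and toxicity-reduced venetoclax doses are pooled with 400 mg

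*SAP*

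**What the plan says.** - **Grouping.** SAP 2.8 sets the rule for all PK endpoints: "Pharmacokinetic endpoints will be analyzed and summarized by dose level of MBG453 (400 mg Q4W, 800 mg Q4W". SAP 2.8.1 applies it to both drugs: "Descriptive summary statistics for MBG453 and venetoclax concentrations will be provided by dose level, visit/sampling time point". No table splits venetoclax by venetoclax dose or by inhibitor use.
- **Listing.** SAP 2.8.1 adds: "MBG453 and venetoclax concentration data will be listed by dose level, subject, and visit/sampling time point". Venetoclax dose and inhibitor use are not named as listing columns.
- **Doses.** Protocol 6.1.1: "Venetoclax film-coated tablets should be administered at a dose of 400 mg orally or corresponding reduced dose for concomitant use with P-gp inhibitors". The steady doses in Table 6-3 are 70 mg with posaconazole ("Reduce venetoclax dose to 70 mg"), 100 mg with another strong CYP3A inhibitor ("Reduce venetoclax dose to 100 mg") and 200 mg with a moderate CYP3A or P-gp inhibitor.
- **Exposure assumption.** SAP 5.1, on venetoclax dose intensity: "By this adjustment, the intended exposure to venetoclax is assumed to remain unchanged from clinical perspective (equivalent to full daily dose 400 mg".
- **Other reductions.** Protocol Table 6-6 allows a lower venetoclax dose, at the investigator's discretion, after clinical TLS or slow-resolving chemistry changes and after repeated Grade 3 or 4 non-hematologic toxicity.
- **Samples.** All scheduled venetoclax samples are pre-dose, on Day 8 of Cycles 1, 3 and 6 (Protocol Table 8-10).

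**The concern.** Venetoclax plasma concentration is a named part of the secondary PK endpoint. The planned grouping factor separates little: SAP 1 reports 85 subjects treated at 800 mg and the Amendment 5 rationale reports 90 enrolled, so about 94% (85/90) fall in one MBG453 level. Protocol 4.3 also regards a clinically relevant interaction with MBG453 as unlikely. The rationale for Amendment 2, by contrast, says that CYP3A4 inhibitors raise venetoclax levels and that azole prophylaxis is common in this population. The factor expected to matter is therefore not in the concentration summary.

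Two things are at stake. The pooled mean represents intended exposure only if the SAP 5.1 assumption is true, and the concentrations that could check it are averaged together. Second, Protocol 12.5.3 treats the C1D8 sample as the venetoclax baseline before any MBG453. The by-visit table invites a comparison of C1D8 with later visits, and a change in inhibitor use between visits would enter that comparison.

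**Working it through.** **1. The SAP's own figure.** The worked example in SAP 5.1 counts 200 mg with an inhibitor as 400 mg.
- Unadjusted: (100+200+300) + 400×25 + 400×28 + 0×14 + 200×42 = 30200 mg.
- Adjusted: the last term becomes 400×42, giving 38600 mg, and 38600/4 = 9650 mg per 28 days.
- Planned: 44200/4 = 11050 mg per 28 days. Ratio: 9650/11050 = 87.33%.

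All figures reproduce. The example shows that the SAP already needs to know when venetoclax was given with an inhibitor. (The example has 300 mg on ramp-up Day 3, where Protocol Table 6-2 has 400 mg. The two must be reconciled. With the Table 6-2 figure the ratio would be 38700/44300 = 87.36%.)

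**2. Dose span.** 400/70 = 5.7, 400/100 = 4 and 400/200 = 2. These are ratios of nominal doses, not of concentrations.

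**3. Effect of pooling on the mean.** Let f be the share of subjects on an inhibitor-adjusted dose. Let R be their mean trough relative to 400 mg without an inhibitor. The pooled arithmetic mean, relative to 400 mg without an inhibitor, is 1 − f + fR. The documents give neither f nor R, so both are assumptions.

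| R | f = 0.2 | f = 0.4 | f = 0.6 |
|---|---|---|---|
| 0.5 | 0.90 | 0.80 | 0.70 |
| 0.8 | 0.96 | 0.92 | 0.88 |
| 1 (SAP 5.1) | 1.00 | 1.00 | 1.00 |
| 1.25 | 1.05 | 1.10 | 1.15 |
| 2 | 1.20 | 1.40 | 1.60 |

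As an extreme, if the inhibitor raised nothing and every adjusted subject took 70 mg, then R = 70/400 = 0.175 and the pooled ratio would be 0.835 at f = 0.2 and 0.505 at f = 0.6. The Amendment 2 rationale contradicts that premise, so it is a bound and not an expectation.

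**4. Effect of a changing mix.** Suppose f rises from 0.2 at C1D8 to 0.6 at C3D8 and nothing else changes. The apparent change is (0.4 + 0.6R)/(0.8 + 0.2R):
- R = 0.5: 0.70/0.90 = 0.78
- R = 1: 1.00
- R = 2: 1.60/1.20 = 1.33

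The mix can change within a subject, because Protocol 6.2.1.1 has the previous venetoclax dosage resumed 2 to 3 days after the inhibitor stops.

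**5. Toxicity-driven reductions.** The equal-exposure statement in SAP 5.1 is tied to inhibitor use, so it does not reach Table 6-6 reductions. The evaluability rule in SAP 2.2 requires the planned dose only for post-dose samples; a pre-dose sample need only precede the next dose. These samples therefore stay in the pooled cells. Their number and size are not in the documents.

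**The case against.** A reader might infer that a cell spanning a 5.7-fold dose range yields a mean that cannot be interpreted. The documents do not support that. The dose is cut because the inhibitor raises venetoclax levels, and SAP 5.1 assumes that the two effects offset. Protocol 6.5.1.2 likewise counts these subjects as having received the planned dose. On that premise nominal milligrams are the wrong scale, and the pooled ratio is 1.00 for any inhibitor share.

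A reader might also infer that inhibitor use is ignored throughout. It is not: SAP 5.1 uses it for cumulative dose and dose intensity, and omits it only from the concentration output.

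It is also fair to say that the stated objective concerns the PK of MBG453, that checking the inhibitor adjustment is no stated aim, and that SAP version 2.0 removed the PK-parameter and DDI analyses. The before-and-after comparison in Protocol 12.5.3 was only optional. The summary reports spread as well as means, and listed values could be linked to dosing and concomitant-medication records.

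All of this limits the consequence but leaves a gap. The equal-exposure statement is an assumption, matched overall exposure does not guarantee matched troughs, and toxicity-driven reductions fall outside it. No planned output fills the gap: SAP 2.8.1 plots concentration-time profiles for MBG453 only, although Protocol 12.5.3 planned them for both drugs.

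**Conclusion.** The point holds as a minor weakness in a descriptive secondary analysis. The pooled venetoclax means reflect intended exposure only if the untested assumption in SAP 5.1 holds for pre-dose concentrations and if toxicity-driven reductions are few or small. A shift in inhibitor use across C1D8, C3D8 and C6D8 could pass for a time or MBG453 effect. No size can be attached from the documents. The ranges in the working (0.70 to 1.60 for the pooled mean, 0.78 to 1.33 for an apparent change between visits) rest on assumed values of f and R, and both include 1.00. No formal test depends on these summaries, and the primary CR analysis is unaffected.

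**What to change.** Keep the planned table in SAP 2.8.1 and add:
1. A summary of venetoclax concentrations by visit and inhibitor category at sampling (none, moderate CYP3A or P-gp, other strong CYP3A, posaconazole), with the MBG453 dose levels pooled.
2. A flag, or a separate row, for samples taken while the venetoclax dose was reduced or interrupted for reasons other than inhibitors, so that inhibitor category alone does not mix doses again.
3. Actual venetoclax dose and inhibitor category as columns in the concentration listing.

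The cost is one descriptive table and two listing columns. Inhibitor co-administration is already needed for the adjusted dose-intensity method in SAP 5.1. The downside is sparse cells: four categories by three visits make 12, and attrition by Cycle 6 will thin them. If the table proves too sparse, the flag and the listing columns still let a reader check the pooled means.

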### 2.8.3 Immunogenicity analysis

Immunogenicity will be characterized descriptively by tabulating ADA prevalence based on the Immunogenicity prevalence set and ADA incidence on-treatment based on the Immunogenicity incidence set.

[figure not shown]
Any IG sample collected after 150 days of the last dose of MBG453 will not be used for summaries or derivations.

ADA prevalence (i.e., ADA-positive samples) will be calculated as the number of ADA-positive samples among the number of subjects with a non-missing sample.

ADA incidence (i.e., ADA-positive subjects) will be calculated as the number of treatment-boosted ADA-positive and treatment-induced ADA-positive subjects among the number of subjects in the Immunogenicity incidence set. Subject ADA status accounted for the ADA incidence are defined as follow:

- Treatment-induced ADA-positive subject: subject with ADA-negative sample at baseline and at least one treatment-induced ADA-positive sample (i.e. ADA-positive sample post-baseline with ADA-negative sample at baseline).
- Treatment-boosted ADA-positive subject: subject with ADA-positive sample at baseline and at least one treatment-boosted ADA-positive sample (i.e. ADA-positive sample post-baseline with titer that is at least the fold titer change greater than the ADA-positive baseline titer).

Further details on the immunogenicity analyses will be provided in separate document at compound level as required.

Frequency

0 20 40 60 80 100

0.0 0.2 0.4 0.6 0.8 1.0

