12.5.3 Pharmacokinetics

The respective PAS for MBG453 and venetoclax will be used in all pharmacokinetic data analysis.

MBG453 and venetoclax drug concentrations

[figure not shown]
MBG453 and venetoclax concentration data will be listed by subject, and visit/sampling time point. Descriptive summary statistics for MBG453 and venetoclax concentrations will be provided by visit/sampling time point. Summary statistics will include mean (arithmetic and geometric), SD, CV (arithmetic and geometric), median, minimum, and maximum, as well as the frequency (n, %) of concentrations below the lower limit of quantification (LLOQ) and reported as zero. Values below the LLOQ will be treated as missing for the calculation of the geometric means and geometric CV%. PK parameters (the minimum observed plasma or serum drug concentration (Cmin or Ctrough) and the maximum (peak) observed plasma or serum drug concentration (Cmax)) will be estimated and reported. Missing values for any PK parameters or concentrations will not be imputed and will be treated as missing.

All concentration data for MBG453 and venetoclax vs. time profiles will be displayed graphically. The concentrations collected before dose administration on Day 8 of Cycle 3 and beyond are Ctrough for MBG453.

As the half life of venetoclax is approximately 26 hours, the sample collected at Cycle 1 Day 8 will be considered as the baseline venetoclax concentration at steady state before any dose administration of MBG453. The impact of MBG453 on the venetoclax concentrations may be assessed by comparing concentrations before and after MBG453.

Population pharmacokinetic analysis

If data permit, a mixed-effects model may be applied to the serum MBG453 concentration-time data from this study along with other studies to generate post-hoc estimates of pharmacokinetic parameters using appropriate software to characterize MBG453 exposure and to determine the effects of intrinsic (i.e. demographic factors) and extrinsic covariates (e.g. combination partners) on MBG453 exposure. If there is sufficient data for analysis, the details of the population pharmacokinetic analyses may be provided in a separate reporting and analysis plan, and the results may be reported in a separate population pharmacokinetic report.

Immunogenicity analysis

Immunogenicity will be characterized descriptively by tabulating ADA prevalence at baseline and ADA incidence on-treatment.

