
 
To assess the CR/CRh rate and the duration of CR/CRh
 
	
 
Proportion of subjects achieving a CR or complete remission with partial hematologic recovery (CRh), as per derivation (Döhner et al 2022)
 
Time from the date of the first CR/CRh to the date of first relapse or progressive disease or death due to any cause, whichever occurs first, as per derivation (Döhner et al 2022)
 

 
To assess the Event-free Survival (EFS)
 
	
 
The time from start of treatment until date of death due to any cause, or relapse from CR, or treatment failure defined as failure to reach CR by Cycle 8 Day 1, whichever occurs first, as per investigator assessment (Cheson et al 2003, Döhner et al 2017)
 

 
To assess Overall Survival (OS)
 
	
 
The time from start of treatment to death due to any cause
 

 
To determine safety and tolerability of MBG453 when administered in combination with azacitidine and venetoclax
 
	
 
Incidence and severity of AEs and SAEs, changes in laboratory values and vital signs, incidence of notable ECG abnormalities
 

 
Characterize the pharmacokinetics (PK) of MBG453 when administered in combination with azacitidine and venetoclax
 
	
 
Pharmacokinetic parameters (serum concentrations for MBG453 and plasma concentrations for venetoclax)
 

 
To evaluate immunogenicity of MBG453 when given in combination of azacitidine and venetoclax
 
	
 
Anti-drug Antibody (ADA) prevalence at baseline and ADA incidence on-treatment
 

 
To assess the effect of MBG453 in combination of venetoclax + azacitidine on transfusion independence
 
	
 
Number and percent of all subjects who achieve transfusion independence on treatment, and from baseline respectively.
 

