### **Immunogenicity (IG) Analysis Sets**

The Immunogenicity prevalence set includes all subjects in the Safety Set with a non-missing baseline IG sample or at least one non-missing post-baseline IG sample.

The Immunogenicity incidence set includes all subjects in the Immunogenicity prevalence set with a non-missing baseline IG sample and at least one non-missing post-baseline IG sample.

A non-missing IG sample indicates a sample that is evaluable and analyzed. Baseline IG sample is the IG sample that was taken before the first administration of MBG453.

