## 4. Change to protocol specified analyses

Not applicable.

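### SAP 2.8.3 defines ADA prevalence as positive samples over subjects with no time point, so as written it does not deliver the endpoint of ADA prevalence at baseline

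*SAP*

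**What the plan says.** The endpoint is the same wherever it is named. Protocol section 12.5.3 states: "Immunogenicity will be characterized descriptively by tabulating ADA prevalence at baseline and ADA incidence on-treatment". Protocol Table 2-1 agrees, and SAP Table 1-1 repeats the endpoint as "Anti-drug Antibody (ADA) prevalence at baseline and ADA incidence on-treatment".

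The SAP's methods text differs. Section 2.8.3 opens by planning to characterise immunogenicity by "tabulating ADA prevalence based on the Immunogenicity prevalence set and ADA incidence on-treatment based on the Immunogenicity incidence set". The qualifier for incidence is kept and the one for prevalence is gone. The calculation follows: "ADA prevalence (i.e., ADA-positive samples) will be calculated as the number of ADA-positive samples among the number of subjects with a non-missing sample".

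The population is set in SAP section 2.2: "The Immunogenicity prevalence set includes all subjects in the Safety Set with a non-missing baseline IG sample or at least one non-missing post-baseline IG sample". Section 2.8.3 has only one time limit, a late one: "Any IG sample collected after 150 days of the last dose of MBG453 will not be used for summaries or derivations".

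SAP section 4, on changes to protocol-specified analyses, reads "Not applicable". The readable part of the SAP document history mentions moving the immunogenicity analysis set into section 2.2 but no new definition of prevalence. Some entries in that history are blacked out.

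**The concern.** Baseline prevalence describes antibodies present before any MBG453. Each subject has one baseline sample, so the natural quantity is a proportion of subjects. The stated rule has samples above the line and subjects below it, and nothing confines either to baseline.

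The choice of samples does not look like a slip of the pen. Section 2.8.3 glosses prevalence as a matter of positive samples and incidence as a matter of positive subjects, and it then defines incidence correctly as subjects over subjects. A programmer who follows the text could reasonably count every positive sample collected up to 150 days after the last MBG453 dose. The figure reported for a named secondary endpoint would then mix pre-existing and on-treatment antibodies and weight each subject by how often that subject tested positive.

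**Working it through.** **No stated figure to reproduce.** Neither document gives an ADA rate, so the check is of the formula.

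**Inputs**
- Scheduled immunogenicity samples per subject (protocol Tables 8-1 and 8-9): Day 8 of Cycles 1, 2, 3, 6, 9, 12, 18 and 24 (8 samples), end of treatment (1), and 30-day and 150-day follow-up (2). Total 8 + 1 + 2 = 11. This is a maximum, because it needs treatment to Cycle 24 and on-site follow-up visits. Unscheduled samples can be added.
- Subjects treated at 800 mg: 85 (SAP section 1).
- Number of ADA-positive subjects and positive samples per subject: not given. Assumed 2% to 20% of 85 subjects ever positive, with 1 to 11 positive samples each. All 85 are assumed to have a sample.

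**Formula under the literal, pooled reading**

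ratio = (positive subjects × mean positive samples per positive subject) / subjects with a sample = ever-positive share × mean positive samples per positive subject

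| Ever-positive subjects of 85 | Ever-positive share | 1 sample each | 4 each | 8 each | 11 each |
|---|---|---|---|---|---|
| 2 | 2.4% | 2.4% | 9.4% | 18.8% | 25.9% |
| 4 | 4.7% | 4.7% | 18.8% | 37.6% | 51.8% |
| 8 | 9.4% | 9.4% | 37.6% | 75.3% | 103.5% |
| 17 | 20.0% | 20.0% | 80.0% | 160.0% | 220.0% |

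The ratio passes 100% once the ever-positive share exceeds 1 divided by the mean number of positive samples. That means 22 subjects with 4 each, 11 with 8 each, or 8 with 11 each; in every case 88/85 = 103.5%.

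**Three different quantities.** The ever-positive share is not the endpoint either. Suppose, purely as an assumption, that 4 of 85 subjects are ever positive with 4 positive samples each, and 1 of the 4 is positive at baseline:
- pooled rule: 4 × 4 / 85 = 16/85 = 18.8%
- ever-positive subjects: 4/85 = 4.7%
- baseline prevalence, the endpoint: 1/85 = 1.2%

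**Under a by-time-point reading.** With one scheduled sample per subject at each time point, positive samples equal positive subjects. Each row is then at most 100%, and the baseline row is 1/85 = 1.2% in the same example.

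**The case against.** The strongest reply is that a table by time point was meant. The incidence denominator names its analysis set, whereas the prevalence denominator is described by having a sample. Everyone in the prevalence set has at least one sample, so under pooling the two descriptions would pick out the same people. A separate phrase makes more sense if the denominator changes from visit to visit. A set defined by "a non-missing baseline IG sample or at least one non-missing post-baseline IG sample" is also what such a table would need. SAP Table 1-1 still names the baseline endpoint, section 2.2 defines the baseline immunogenicity sample, and 2.8.3 defers further detail to a compound-level document that is not available here.

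This makes the by-time-point reading plausible but does not put it in the plan. Section 2.8.1 says explicitly that concentrations are summarised by visit or sampling time point; 2.8.3 says nothing of the kind for prevalence. A deferred document may clarify the formula but does not replace the one the SAP states.

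Two further points stand. The values above 100% are corner cases: 11 positive samples require positivity before any MBG453, dosing to Cycle 24 and a 150-day on-site sample. A percentage above 100% would also be noticed in the output. A more moderate inflation, such as 4.7% reported as 18.8%, would not be obvious.

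**Conclusion.** The definition in SAP 2.8.3 does not, as written, produce the baseline prevalence named in the protocol and in the SAP's own Table 1-1. Only a by-time-point reading that the text does not state would rescue it, and section 4 declares no departure.

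The size cannot be fixed from the documents. Under pooling, the overstatement relative to the ever-positive share equals the mean number of positive samples per positive subject, assumed to lie between 1 and 11. Relative to true baseline prevalence it can be larger, because on-treatment positives also enter.

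A reader might infer that the reported figure will be inflated, or that the SAP has abandoned the baseline endpoint. The documents support neither. Inflation follows only if samples are pooled, and Table 1-1 keeps the endpoint. Nor does the point reach the main conclusions: immunogenicity is secondary and descriptive, with no test or success rule attached, and the CR and DLT analyses do not use it. Severity is low.

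**What to change.** Replace the prevalence sentence in SAP 2.8.3 with a definition of baseline ADA prevalence, by dose level: the number of subjects whose baseline immunogenicity sample is ADA-positive, divided by the number with an evaluable, analysed baseline sample. Refer to the immunogenicity-specific baseline in section 2.2 (before the first MBG453 dose). The general baseline in Appendix 5.1 is tied to the start of any study treatment, whereas the first immunogenicity sample is scheduled at Cycle 1 Day 8.

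If post-baseline or any-time prevalence is also wanted, either tabulate it by time point or define it as subjects with at least one positive sample over subjects in the prevalence set. Label it separately from the endpoint and list it in section 4 as an addition.

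The cost is one or two sentences and a change of numerator and denominator in one table program. No new data are needed.
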